6. STUDY POPULATION

6.1 INCLUSION CRITERIA

Pregnant women with a singleton or twin pregnancy who have pre-gestational diabetes OR gestational diabetes.

AND

plan to give birth by elective CS between 35⁺⁰ and 39⁺⁶ weeks gestation (randomisation can occur within the week prior to 35⁺⁰).

AND

The CS is scheduled between 24 hours and 7 days from the time of randomisation.

Pre-gestational diabetes is defined (for the purposes of this trial) as either Type 1 or Type 2 diabetes that was diagnosed prior to the start of the pregnancy (regardless of whether the patient received medication for the diabetes prior to the start of the pregnancy).

Gestational diabetes is defined in Australia as an abnormal pregnancy 75 g Oral glucose tolerance test according to the WHO criteria for gestational diabetes.⁶¹ Gestational diabetes is defined in New Zealand according to the Ministry of Health.⁶² Gestational diabetes may also be diagnosed in either country via the modified criteria for diagnosis of gestational diabetes during the COVID-19 pandemic recommended by Royal Australian New Zealand College of Obstetricians and Gynaecologists and Australasian Diabetes in Pregnancy Society.⁶³

WHO criteria for diagnosis of gestational diabetes or diabetes in pregnancy⁶¹ :

- a) Gestational diabetes mellitus should be diagnosed at any time in pregnancy if one or more of the following criteria are met:
 - fasting plasma glucose 5.1-6.9 mmol/l
 - one hour plasma glucose \geq 10.0 mmol/l following a standardised 75g oral glucose load
 - two hour plasma glucose 8.5-11.0 mmol/l following a 75g oral glucose load

- b) Diabetes mellitus in pregnancy should be diagnosed if one or more of the following criteria are met⁶¹ (however for the purposes of this trial, these participants will be classified as gestational diabetes):
 - fasting plasma glucose \geq 7.0 mmol/l
 - two hour plasma glucose \geq 11.1 mmol/l following a 75g oral glucose load
 - a random plasma glucose \geq 11.1 mmol/l in the presence of diabetes symptoms

New Zealand Ministry of Health⁶² criteria for gestational diabetes:

- fasting plasma glucose ≥ 5.5 mmol/L
- two hour post-prandial plasma glucose ≥ 9.0 mmol/L following a 75g oral glucose load

The modified criteria for diagnosis of gestational diabetes during the COVID-19 pandemic recommended by Royal Australian New Zealand College of Obstetricians and Gynaecologists and Australasian Diabetes in Pregnancy Society:⁶³

- Early pregnancy: HbA1c $\geq 5.9\%$ OR Random blood glucose (RBG) ≥ 9.0 mmol/L
- 24 -28 weeks' gestation: Fasting plasma glucose ≥ 5.1 mmol/L (Fasting plasma glucose < 4.7 excludes the diagnosis of gestational diabetes. A formal glucose tolerance test is recommended for women with a fasting plasma glucose between 4.7-5.1)

6.2 EXCLUSION CRITERIA

- Known major fetal anomaly or chromosomal anomaly
- Administration of intramuscular antenatal corticosteroids (for fetal lung maturity) at any time during the pregnancy prior to randomisation
- Maternal systemic fungal infection
- Maternal thrombocytopenia with a platelet count below 80×10^9 /litre
- Hypersensitivity to betamethasone sodium phosphate, betamethasone acetate, or other corticosteroids
- Other contraindications to corticosteroids
- Prior participation in the PRECeDe trial in a previous pregnancy (prior participation in the PRECeDe Pilot trial is NOT regarded as an exclusion from participation in the current trial)

6.3 CONSENT

Women will be identified and counselled by trained research staff under the supervision of the Principal investigator at each site. A patient information and consent form will be provided. Written consent or e-consent via REDCap will be obtained.

We seek a waiver of consent to screen patients for eligibility and collect deidentified data regarding the number of eligible participants, the number approached, and the number of participants who decline to participate consistent with the recommendations in the CONSORT statement.⁶⁰

7. PARTICIPANT SAFETY AND WITHDRAWAL

7.1 PARTICIPANT RISK MANAGEMENT AND SAFETY

Risk One: Potential for the trial to increase the CS rate and risks related to CS.

Women will be planning to undergo an elective CS. The decision to perform a CS and the timing of that procedure is made prior to inclusion in the study and as such the risks of this procedure are separate to the risks related to this trial. All women will receive formal advice from a hospital medical officer to allow them to give informed consent to the CS.

Risk Two: Potential for Maternal Harm

At present, there is no definitive evidence of risks associated with antenatal corticosteroid use in the manner described in this protocol. Women will be informed of the potential side effects which include pain, swelling and bruising at the injection site and maternal hyperglycaemia. The risks of maternal hyperglycaemia will be mitigated by regular assessment of the maternal blood glucose. In addition, we will ensure that there are always staff available at each participating site 24 hours a day, 7 days a week to provide telephone advice regarding management of maternal hyperglycaemia if this occurs.

Risk Three: Potential for Neonatal Hypoglycaemia

Neonatal hypoglycaemia is common in infants born to women with diabetes. Consistent with recommended practice, all infants will undergo neonatal blood glucose monitoring and treatment of hypoglycaemia. Recent evidence suggests that the detection and treatment of hypoglycaemia is not associated with any additional risks compared with infants at risk of hypoglycaemia who do not develop hypoglycaemia.⁶⁴

Risk Four: Potential for longer term harms

Concerns have been raised about possible longer-term effects of antenatal corticosteroids on childhood development, including possible effects on learning, behaviour and psychological health.¹⁷ Raikonen et al reported a modest increase in the overall risk of psychological disorders in those who were exposed to antenatal corticosteroids, however, it is important to note that in this cohort study, corticosteroids were generally prescribed to those deemed 'at risk' of preterm birth (rather than within 7 days prior to planned CS birth after 35⁺⁰ weeks) and the corticosteroid exposed group were more likely to have premature rupture of membranes (16.7% vs 2.7%), hypertensive disorders (10.3% vs 4.0%), and maternal psychiatric disorders (26.7% vs 18.4%), and those born after 37 weeks had a significantly lower mean birth weight than their non-exposed counterparts (2659 ± 950 g vs 3548 ± 496g) – factors which themselves are associated with increased risks of adverse neurocognitive outcome.¹⁷ Thus, the strength of the association between corticosteroids and adverse psychological outcomes remains uncertain. Importantly, this study did not demonstrate any association between antenatal corticosteroids and moderate (RR 0.96, 95% CI 0.64, 1.42, p=0.55) or severe / profound (RR 1.17, 95% CI 0.37, 3.69, p=0.53) intellectual impairment amongst those infants exposed to corticosteroids prior to 35 weeks but who were then born at term (after 37 weeks).¹⁷

While the assessment of longer term neurocognitive outcomes is beyond the scope of this trial, we will maintain contact with the cohort to ensure that these outcomes can be formally evaluated within the context of this randomised trial.

7.2 HANDLING OF WITHDRAWALS

Participants who choose to withdraw from the study will be invited to continue to provide data for the study including birth and neonatal outcome data as well as participation in the postnatal surveys at 6 weeks. Should they decline to contribute any data to the study, they will have the option to either retain existing data in the database (data collected prior to the withdrawal) or have their data deleted from the database and they will be regarded as a complete withdrawal from the study.

7.3 REPLACEMENTS

To preserve the statistical power of this trial, replacements will be permitted equivalent to the number of participants who withdraw from the trial.

7.4 TRIAL RISKS

Trial Risk One: Potential for unblinding of participants and staff

We will collect data regarding whether participants, clinicians and research staff remain blinded to the treatment allocation for a subset of participants. These data will only be collected in the event of (i) slow recruitment (see Trial Risk 2) or (ii) projected budget shortfalls (see Trial Risk 3). Data will be analysed prior to completion of the trial to determine whether the trial should pivot to an open label trial (ie betamethasone would be prescribed on site for participants allocated to betamethasone and participants, clinicians and research staff would be aware of the treatment allocation). The decision to pivot to an open trial will be made by the Trial Steering Committee if the Kappa statistic for participants, postnatal clinicians or research staff is above 0.41 (indicating moderate agreement between the participant, clinician or research staff and the true treatment allocation). Regardless of the success of blinding in the perinatal period, children would be assessed for outcomes in later childhood by health professionals who are unaware of their treatment group allocation; it is the later childhood outcomes that will be critical in determining the balance between risks and benefits of ACS.

Trial Risk Two: Slow recruitment

Given the pace of change in obstetric and neonatal practice, it is important that this trial is completed in a timely manner – with recruitment to be completed within the 5 year time frame. We will review recruitment progress every 6 months to consider strategies to improve recruitment. Recruitment targets will be established by the Trial Steering Committee at the time of activation of the first recruiting site(s). If recruitment is less than 80% of the expected target at 2 consecutive timepoints, the trial steering committee will consider the need to analyse the blinding assessment data (described in Trial Risk One) to determine whether the trial should pivot to an open label trial to allow a greater number of sites to participate.

Trial Risk Three: Budget shortfalls

While the research team have considerable expertise in managing research budgets, the requirement to use external suppliers for supply and packaging of investigational product together with the significant increase in the costs associated with regulatory authorities and freight may adversely affect the budget. Where a budgetary shortfall is anticipated, the Trial Steering Committee may request analysis of data collected regarding the ability to maintain blinding to determine if pivoting to an open label trial might help to reduce the costs associated with the trial.

8. STATISTICAL METHODS

8.1 SAMPLE SIZE ESTIMATION & JUSTIFICATION

A sample size of 2200 mothers (1100 in each arm, with continuity correction and allowing for 3% drop-out) will have 90% power to detect a relative reduction of 50% (absolute reduction of 3%) in neonatal respiratory distress from 6% to 3% with two-sided alpha of 0.05. This sample size will provide over 80% statistical power to detect a clinically significant increase of 30% in the secondary outcome of neonatal hypoglycaemia requiring treatment other than feeding

from 16% (from our pilot data for gestational diabetes and pre-gestational diabetes) to 20.8%.^{50,65}

We have used the following to inform our sample size:

- The effect size for the primary outcome of 50% reduction in rate of respiratory distress is based on the ASTECS study (RR 0.46, 95% CI 0.23 – 0.93),³⁷ and is consistent with the effect size observed in the meta-analysis of antenatal corticosteroids for late preterm and term infants (RR 0.74 95% CI 0.61 – 0.91 overall and RR 0.40, 95% CI 0.27 – 0.59 when the analysis is restricted to those delivering by planned CS after 37 weeks).⁶⁶ We consider a 50% reduction in the rate of respiratory distress requiring intervention for ≥ 60 minutes to be clinically relevant and likely to result in significant cost savings by preventing admissions to the neonatal nursery.
- The baseline prevalence of respiratory morbidity in neonates born to mothers with pre-gestational and gestational diabetes is estimated at 6% based on our preliminary studies from Sunshine Hospital and The Royal Women's Hospital. We have allowed for the higher prevalence of respiratory morbidity in babies born to women with pre-gestational diabetes (9% - Table 1) than to women with gestational diabetes (3-10%), but the lower prevalence of pre-gestational diabetes than that of gestational diabetes. This prevalence of respiratory morbidity is consistent with that observed in the ASTECS trial³⁷ (baseline prevalence of respiratory distress of 5.1%) and in the meta-analysis of antenatal corticosteroids in late preterm and term infants (7.2% in controls).⁶⁶

8.2 STATISTICAL METHODS TO BE UNDERTAKEN

We will undertake descriptive statistical analysis reporting the proportion of women screened, eligible, approached, consented and refused as well as the time taken to complete study procedures.

Outcomes will be compared between the intervention and control groups using an intention-to-treat analysis. For all binary outcomes the magnitude of the between-group differences will be quantified by fitting a logistic regression model to estimate the odds ratio (OR) and 95% confidence interval (CI) for the corresponding population OR, stratified by recruitment site, type of diabetes (Type 1 diabetes, Type 2 Diabetes, Gestational Diabetes), and gestation at planned elective CS (35⁺⁰ to 36⁺⁶ weeks, 37⁺⁰ to 38⁺⁶ and 39⁺⁰ to 39⁺⁶ weeks). Linear regression will be used for non-categorical outcomes. For infant outcomes models will be fitted using Generalised Estimating Equations to allow for non-independence of outcomes among twins from the same pregnancy.

Assessment of blinding will be undertaken using Kappa statistic to assess the correlation between the participant or staff members "guess" of the allocation and the true allocation.

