4. OUTCOME MEASURES

Primary outcome: Respiratory morbidity, defined as requiring admission to the neonatal nursery and any form of respiratory support (e.g. intermittent positive pressure via an endotracheal tube, nasal continuous positive airway pressure (CPAP), Hi- or Lo-flow oxygen/air mixture, or increased ambient oxygen delivered into an incubator) for ≥ 60 minutes at any time following birth.

Secondary outcomes:

For the infant:

- hypoglycaemia defined as any blood glucose concentration < 2.6 mmol/l;

- hypoglycaemia requiring treatment other than milk feeding (including dextrose gel, intravenous dextrose, glucagon);
- admission to a neonatal nursery and length of stay;
- severity of respiratory distress (severe: any intubation/mechanical ventilation and/or need for surfactant therapy; moderate: respiratory support (sum of mechanical and non-invasive) required for >24 hours; mild: the remainder requiring respiratory support for ≥60 minutes but <24 hours). The maximum appropriate mean airway pressure [MAP] for those requiring mechanical ventilation or nasal CPAP, and maximum appropriate fractional inspired oxygen [FiO₂] for those requiring any form of respiratory support will also be recorded. For those on HiFlo, the maximum appropriate flow rate will be recorded.
- need for, and duration of, all forms of respiratory support (including all forms of respiratory support described in the primary outcome);
- use of exogenous surfactant;
- pneumothorax or air leak requiring drainage;
- presence of x-ray features suggestive of hyaline membrane disease or transient tachypnoea of newborn (independently adjudicated by a neonatal radiologist blinded to treatment allocation) in a subset of babes who require chest x-ray as part of clinical care.

For the mother:

- requirement for additional insulin therapy after administration of study drug;
- requirement for hospital admission between randomisation and CS;
- highest blood glucose concentration recorded between randomisation and birth;
- maternal infection from the time of randomisation up until 6 weeks' postpartum including chorioamnionitis; maternal pyrexia ≥38°C; wound infection requiring antibiotic or surgical /radiological (e.g. ultrasound-guided drainage) treatment;
- maternal reported side effects of the study drug;
- maternal mental health assessed using the Edinburgh Postnatal Depression scale (EPDS);^{56,57}

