5.1 STUDY TYPE & DESIGN & SCHEDULE

The PRECeDe Randomised Trial is an international multicentre, randomised, triple blind, placebo controlled trial (Figure 4).

Trial setting: The trial will be conducted in maternity units throughout Australia and New Zealand

Trial entry: Women will be identified and counselled by trained research midwives. Written consent will be obtained. In accordance with the CONSORT statement⁶⁰ we will collect data regarding the number of eligible participants, the number approached, and the number of participants who decline to take part in the trial via a waiver of consent to collect deidentified data regarding potentially eligible participants.

Randomisation: Eligible, consenting women will be randomised using a computer generated random number sequence. The randomisation schedule, using a 1:1 randomisation and variable block size will be prepared in advance.

Randomisation will be stratified by:

- Type of diabetes (Type 1 diabetes, Type 2 Diabetes, Gestational Diabetes)
- Gestation at delivery (35⁺⁰ to 36⁺⁶ and 37⁺⁰ to 38⁺⁶ weeks, 39⁺⁰ to 39⁺⁶ weeks)
- Recruiting site

Randomisation can only take place within 7 days prior to planned elective CS and at least 24 hours prior to planned elective CS to allow two doses of betamethasone to be administered prior to birth. Randomisation can occur within the week prior to 35⁺⁰ weeks gestation as long as the planned CS is scheduled after 35⁺⁰ weeks gestation.

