After discharge of the mother and baby from hospital after the birth, the health outcome data will be collected from the case records by the research midwife at the recruiting centre and entered into a purpose built REDCap database.

Women and their children will be followed up after discharge from hospital with questionnaires regarding additional maternal morbidity (wound infections, mental health) and neonatal morbidity (respiratory illness, method of feeding, and feeding difficulties) completed at 6 weeks' postpartum. In addition we will collect health information via the standardised SF12, EPDS and the AQoL-8D. Women who score ≥ 13 on the EPDS will be contacted by the lead investigator / trial coordinator at the respective site to assess maternal well being and will be directed to appropriate resources according to local guidelines.

All data will be entered into a REDCap database stored on a secure password protected server at The University of Melbourne.

Childhood Follow-Up: We will seek permission for on-going contact at least annually with mothers and their infants as part of the consent process. This contact will take the form of an email message with an annual 'birthday card' sent to the email address as well as an SMS request to update participant contact details. Future childhood follow-up studies are planned and separate funding will be sought to undertake these studies. All future studies will require HREC approval.

Emergency Unblinding: Unblinding is unlikely to be required for management of a participant with an adverse event as the effect of antenatal corticosteroids is generally short lived. However, emergency unblinding will be possible and can be arranged by contacting the Trial Coordinator or Coordinating Principal Investigator.

STUDY TABLE

Procedures	Assessment / Procedure	Screening (after 32 weeks)	Randomisation (within 7 days of planned elective CS)	First dose of betamethasone or placebo	Second Dose of Betamethasone or placebo (24 hours after first dose)	Caesarean Section and Post birth visit / data collection	Discharge of mother and baby	6 week follow-up	Annual follow-up
	Informed Consent	X							
	Demographic Information Weight & Height Measurement		X						
	Administration of Betamethasone or placebo			X	X				
	Symptoms questionnaire					X		X	
	Completion of EPDS, SF12, AQuOL 8D		X					X	
	Collection of data about blood glucose measurements and insulin doses			X	X	X			
	Collection of birth and neonatal data					X	X		

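### Section 8.2 states adjustment for the randomisation strata only for binary outcomes and gives no use for the EPDS, SF-12 and AQoL-8D scores collected at randomisation

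*Protocol*

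**What the plan says.** **Collection.** The study table in the Protocol, section 5.1, has a row "Completion of EPDS, SF12, AQuOL 8D", marked at randomisation and at the 6-week follow-up. The data collection text in the same section confirms the later time: "In addition we will collect health information via the standardised SF12, EPDS and the AQoL-8D". Section 4 lists general health on SF-12 and AQoL-8D both before randomisation and at 6 weeks. It lists EPDS as a maternal outcome without a time point and without saying whether it is analysed as a score or at a cut-off.

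**Randomisation.** Section 5.1 allocates "using a 1:1 randomisation and variable block size". Under "Randomisation will be stratified by" it lists type of diabetes, gestation and recruiting site.

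**Analysis.** Section 8.2 says: "For all binary outcomes the magnitude of the between-group differences will be quantified by fitting a logistic regression model". That same sentence ends with the clause "stratified by recruitment site, type of diabetes (Type 1 diabetes, Type 2 Diabetes, Gestational Diabetes), and gestation at planned elective CS". The next sentence stands alone: "Linear regression will be used for non-categorical outcomes". The synopsis makes the same split. Neither place names a covariate for the linear models or says how the scores at randomisation enter the analysis.

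**The concern.** The protocol settles adjustment for one class of outcome and stops short for the other, although the same stratified randomisation underlies both. An analyst who follows section 8.2 literally could fit linear models containing only the treatment term. Two pieces of information already in the database would then go unused.

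- The score at randomisation, for EPDS, SF-12 and AQoL-8D. It is usually the strongest predictor of the later score on the same instrument.
- The randomisation strata. When strata relate to the outcome but are left out of the model, the reported standard error is generally too large.

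At stake is the width of the confidence intervals for maternal mental health and quality of life. There is also an ambiguity: with both time points listed inside the SF-12 and AQoL-8D outcome, a reader cannot tell whether the 6-week score, the change, or a baseline-adjusted 6-week score will be compared.

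**Working it through.** **1. The plan's own figure.** The protocol gives no standard deviation, effect size or power for the questionnaire scores. Its sample size concerns the primary outcome: 6% versus 3%, 90% power, two-sided alpha 0.05, continuity correction, 3% drop-out (section 8.1). The two-proportion formula gives 1002 per arm without continuity correction and 1068 with it. Then 1068 / 0.97 rounds up to 1102 per arm, or 2204 in total, against the stated 2200. The stated figure reproduces and is not in question.

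**2. Inputs for the questionnaire scores.**

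- Analysed per arm: 1100 × 0.97 = 1067, taking the protocol's 3% drop-out to apply at 6 weeks.
- Correlation r between the score at randomisation and at 6 weeks: not in the protocol. Assumed, over 0.3 to 0.7.
- Share of outcome variance explained by the strata: not in the protocol. Assumed, 1% to 5%.

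**3. Without covariates.** In units of the outcome's standard deviation (SD), SE = √(2/1067) = 0.0433. The 95% half-width is 1.96 × 0.0433 = 0.085 SD. The difference detectable with 80% power is (1.960 + 0.842) × 0.0433 = 0.121 SD.

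**4. With the baseline score in the model.** The variance of the treatment effect is multiplied by 1 − r² and the SE by √(1 − r²).

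| Assumed r | 1 − r² | Variance cut | SE cut | 95% half-width (SD) | Detectable at 80% power (SD) | Power for 0.10 SD |
|---|---|---|---|---|---|---|
| none | 1.00 | – | – | 0.085 | 0.121 | 64% |
| 0.3 | 0.91 | 9% | 5% | 0.081 | 0.116 | 68% |
| 0.5 | 0.75 | 25% | 13% | 0.073 | 0.105 | 76% |
| 0.7 | 0.51 | 49% | 29% | 0.061 | 0.087 | 90% |

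Seen the other way, leaving the baseline score out inflates the variance by 1/(1 − r²): 1.10, 1.33 and 1.96 at the three values of r. The percentage cuts do not depend on the number analysed. The half-widths, detectable differences and powers do.

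**5. With the strata alone.** The SE is multiplied by √(1 − R²): √0.99 = 0.995 and √0.95 = 0.975, which is about 0.5% to 2.5% off the SE. For these scores nearly all the gain comes from the baseline score.

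**The case against.** The strongest objection is that section 8.2 is silent and does not exclude anything. Baseline-adjusted analysis is itself linear regression, so the quoted sentence is compatible with the better model, and listing both time points for SF-12 and AQoL-8D may even suggest that the baseline will be used. Covariates for secondary continuous outcomes are commonly left to the statistical analysis plan, which is not shown. This stands against any claim that the plan leaves out the baseline score or the strata, or that precision will in fact be lost. It does not remove the asymmetry: the protocol does name adjustment factors for binary outcomes, in two places, and stops there. An analysis plan faithful to that text could properly fit unadjusted linear models.

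Four further limits stand.

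- The unadjusted estimate is unbiased under randomisation, and omitting the strata errs on the conservative side.
- The size of the gain rests on a correlation that the protocol does not give.
- EPDS may be analysed at a cut-off. The protocol uses 13 or more as the trigger for contacting the participant. If EPDS is analysed as binary, the logistic model with its strata already covers it.
- A reader might infer that highest maternal glucose suffers most, because it plausibly depends on diabetes type. The protocol gives no glucose figures by diabetes type, so that cannot be sized and is not claimed here.

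**Conclusion.** The point holds as a gap in what section 8.2 and the synopsis specify. Strata are stated for binary outcomes and not for continuous ones, and the scores collected at randomisation have no stated use. If the linear models were fitted without covariates, the questionnaire comparisons would be valid but wider than necessary. The variance would be higher than needed by a factor of 1.10 to 1.96 for assumed r between 0.3 and 0.7. The strata matter little for these scores, but including them would bring the linear models into line with the design and with the binary models.

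A reader might go further and infer that the trial has chosen an unadjusted analysis, or that its conclusions are at risk. The document supports neither. It excludes no covariate, and these are secondary outcomes with no power claim. The primary outcome and the total of 2200 are untouched. This is an improvement available at no cost, not a correction of an error.

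**What to change.** In section 8.2 and the synopsis, replace the sentence on linear regression with:

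*Continuous outcomes will be analysed by linear regression adjusted for the stratification factors and, for SF-12, AQoL-8D and EPDS where analysed as a score, the score at randomisation.*

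The existing provision for twins (generalised estimating equations for infant outcomes) stays as it is. The cost is one sentence in two places, agreed before unblinding. No new data, visits or participants are needed, because the scores and the strata are already collected.
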